**A Phase 2, Randomized, Multi-institutional Study of Nivolumab and Ipilimumab
versus Nivolumab, Ipilimumab and Stereotactic Body Radiation Therapy for
Metastatic Merkel Cell Carcinoma**

NCT03071406

Version 11

January 26, 2023

Clinical Protocol

A Phase 2, Randomized, Multi-institutional Study of Nivolumab and Ipilimumab versus Nivolumab, Ipilimumab and Stereotactic Body Radiation Therapy for Metastatic Merkel Cell Carcinoma

PI: [name], PhD

Co-PI: [name]

Co-Investigator: [name]

Co-Investigator: [name], PhD

Co-Investigator: [name]

Co-Investigator: [name]

Co-Investigator: [name]

Co-Investigator: [name], PhD

Biostatistician: [name]

Pathologist: [name]

Radiologist: [name]

OSU Site PI: [name]

Collaborating Institutions:

Ohio State University James Cancer Hospital and Solove Research Institute

DOCUMENT HISTORY

Document	Date of Issue	Summary of Change
Original Protocol		Not applicable

SYNOPSIS

Clinical Protocol

Protocol Title: A Phase 2, Randomized, Multi-institutional Study of Nivolumab and Ipilimumab versus Nivolumab, Ipilimumab and Stereotactic Body Radiation Therapy for Metastatic Merkel Cell Carcinoma.

Investigational Product(s), Dose and Mode of Administration, Duration of Treatment with Investigational Product(s):

Stereotactic Body Radiation Therapy 24Gy in 3 fractions.

Nivolumab 240 mg/dose IV q2 weeks.

Ipilimumab 1 mg/kg/dose IV q6 weeks.

Treat subjects until disease progression, unacceptable toxicity or subject withdrawal of consent.

Study Phase: 2

Research Hypothesis: Treatment with nivolumab and ipilimumab, or nivolumab and ipilimumab in combination with stereotactic body radiation therapy (SBRT) will improve objective response rate as compared to nivolumab alone historical control in subjects with metastatic Merkel cell carcinoma.

Objectives:

Primary:

- To compare the efficacy, as measured by objective response rate (ORR), provided by nivolumab plus ipilimumab with or without SBRT in subjects with metastatic Merkel cell carcinoma.

[figure not shown]
Secondary:

- To compare the progression free survival (PFS) of nivolumab and ipilimumab versus SBRT plus nivolumab and ipilimumab in subjects with metastatic Merkel cell carcinoma.
- To compare the overall survival (OS) of nivolumab and ipilimumab versus SBRT plus nivolumab and ipilimumab in subjects with metastatic Merkel cell carcinoma.
- To evaluate the local control of irradiated tumor provided by SBRT in combination with nivolumab and ipilimumab
- To assess the overall safety and tolerability of nivolumab and ipilimumab versus SBRT plus nivolumab and ipilimumab in subjects with metastatic Merkel cell carcinoma.
- To evaluate whether PD-L1 expression is a predictive biomarker for ORR.
- To evaluate the Health Related Quality of Life (HRQoL) as assessed by European Organisation for Research and Treatment of Cancer (EORTC) QLQ-C30.

Exploratory: See [Section 1.3.3](#) of the protocol.

Study Design:

This is a Phase 2, randomized, multi-institutional study of nivolumab and ipilimumab alone versus in combination with SBRT for subjects (≥ 18 years) with metastatic Merkel Cell Carcinoma. Approximately 50 subjects will be randomized 1:1 and stratified by prior immunotherapy exposure. Dose reductions will not be allowed.

Treatment Arms:

Randomized 1:1 [Arm A: Arm B]: Treatment until progression on either arm.

Arm A:

Nivolumab 240 mg IV over 30 min q2 weeks and Ipilimumab 1 mg/kg IV over 30 min q6 weeks until progression or unacceptable toxicity

Arm B:

Nivolumab 240 mg IV over 30 min q2 weeks and Ipilimumab 1 mg/kg IV over 30 min q6 weeks until progression or unacceptable toxicity

Radiation to be given at the start of week 2

- 8 Gy x3 doses in over ≤ 2 weeks

SBRT should begin the week following the first dose of nivolumab and ipilimumab. All sites other than skin should receive SBRT in consecutive days. Skin lesions can be treated every other day.

The number of lesions receiving SBRT will be at the treating physician's discretion based on anticipated toxicity. Larger or symptomatic lesions are of higher priority for SBRT. At least one target lesion will not receive SBRT, to evaluate ORR. The scatter radiation dose to this target lesion should be monitored if located less than 6cm from the irradiated lesions.

All subjects will be treated until progression of disease, unacceptable toxicity, or subject withdrawal of consent. Palliative radiation therapy will not be permitted while being treated under the protocol. The need for palliative radiation therapy will be considered progressive disease.

Study Population: Metastatic Merkel cell carcinoma subjects

Key Inclusion Criteria:

- At least 18 years of age
- ECOG PS < 2
- Active disease measurable by CT or MRI.
- Prior chemotherapy or immunotherapy will be allowed if new or persistent measurable site(s) of disease are present.
- Prior radiation therapy will be allowed if there is active measurable disease burden.
- All subjects must be either recurrent, unresectable or Stage IV AJCC (7th edition) and have histologically confirmed Merkel cell carcinoma with at least 2 distinct lesions in order to be eligible. Please refer to [Appendix 1](#) for description of AJCC 7th editions of TNM and staging.

- All subjects must have at least 2 distinct lesions as documented by a complete physical examination or imaging studies within 4 weeks prior to randomization. Imaging studies must include a diagnostic CT scan of the involved disease sites and all known sites of resected disease and brain magnetic resonance (MRI) or CT (brain CT allowable if MRI is contraindicated or if there is no known history of resected brain lesions).
- Tumor tissue from the core biopsy or resected site of disease must be provided for biomarker analyses.

Key Exclusion Criteria:

- Subjects with history of Grade 3 toxicity or use of infliximab with prior immunotherapy
- Patients with active brain metastasis.
- Subjects with active, known, or suspected autoimmune disease. Subjects with type I diabetes mellitus, residual hypothyroidism due to autoimmune thyroiditis only requiring hormone replacement, skin disorders (such as vitiligo, psoriasis, or alopecia) not requiring systemic treatment are permitted to enroll.
- Subjects with prior history of non-Merkel cell carcinoma malignancies are excluded except adequately treated basal cell, squamous cell skin cancer, chronic lymphocytic leukemia or other indolent diseases not requiring therapy; adequately treated, with curative intent, cancer from which the patient is currently in complete remission per investigator’s judgment; or patients with history of breast cancer and no evidence of disease on hormonal therapy to prevent recurrence and patients with prostate cancer on adjuvant hormonal therapy with undetectable PSA are eligible.
- Subjects with a condition requiring systemic treatment with either corticosteroids (> 10 mg daily prednisone equivalent) or other immunosuppressive medications within 14 days of randomization. Inhaled or topical steroids are permitted in the absence of active autoimmune disease.

Study Drug:

Study Drug		
Medication	Potency	IP/Non-IP
Nivolumab Solution for Injection	100 mg (10 mg/mL)	IP
Ipilimumab Solution for Injection	50 mg (5 mg/mL)	IP

Study Assessments: Objective response rate is the primary endpoint of the trial. The ORR will be calculated as the percentage of patients who had a complete or partial response that was confirmed by a subsequent radiologic imaging study or clinical exam according to irRECIST criteria among all the patients who received at least one dose of nivolumab and ipilimumab with or without SBRT.

- Screening.
- Treatment Period: Every 12 weeks (\pm 7 days) from first dose of study drug through 45 weeks (relative to the first dose of study drug)
- Follow-up Period:
 - a) Every 12 weeks (\pm 14 days) through 12 months for subjects who discontinued early from treatment (relative to the first dose of study drug)

- b) Every 12 weeks (± 21 days) if > 12 months through 24 months (relative to the first dose of study drug)
- c) Every 6 months (± 28 days) if > 24 months through and up to Year 5 (relative to the first dose of study drug).

Statistical Considerations:

Sample Size: From historical data, we will consider 17% response rate as not warranting further study. We will use 40% response rate as a promising result to pursue further study. In other words, we are interested in at least 23% (40% vs. 17%) improvement in treatment efficacy for arms B versus A. For each arm, using a Simon Mini-Max two-stage design with 10% type I error rate and 10% type II error rate, 16 patients will be enrolled in the first stage of the trial. If 2 or fewer patients respond, the treatment will be stopped. If 3 or more patients show a response, 8 additional patients (a total of 24 patients per group) will be enrolled. If the total number responding is 6 or less, we will conclude that the treatment is not effective. If both arms fail at the first or second stage, the trial will stop. No winner will be claimed. The sample size will be 32 if both arms fail at the first stage and 40 if only one arm fails at the first stage. If only one arm pass the second stage, the arm will be the winner. If both arms pass the second stage, we will use the posterior probability, $\Pr(B>A)$, (probability of the response rate in arm B higher than in arm A) to select the winner. A non-informative prior of beta distribution, $\text{beta}(1,1)$ in both arms will be used to calculate the posterior probability. Arm B will be claimed as the winner if $\Pr(B>A) > \delta = 0.8$.

Endpoints:

Primary Endpoint: Objective response rate in all randomized subjects

Secondary Endpoint: Progression free survival and overall survival

Analyses: Patient demographics and toxicity will be summarized using descriptive statistics. Hematologic and non-hematologic toxicity will be analyzed by CTCAE criteria and compared between treatment groups using Pearson's Chi-square test. All tests will be two-sided with an α (type I) error ≤ 0.05 considered to be statistically significant. Continuous variables will be described by number of patients, mean, standard deviation, median, minimum and maximum. Categorical variables will be tabulated using frequency counts and percentages. The primary analysis of ORR in all randomized subjects will be conducted using a two-sided log-rank test. The hazard ratio and corresponding two-sided 95% confidence interval (CI) will be estimated using a Cox proportional hazards model, with treatment arm as a covariate. PFS medians with 95% CIs and PFS rates at 6, 12, 24, and 36 months with 95% CIs will be estimated using Kaplan-Meier methodology.

Stopping criteria: A Safety Monitoring Committee will be formed to evaluate the toxicity of both arms. Interim analysis will be conducted following accrual of initial cohort of patients in the Simon's two stage design to determine whether SBRT introduces excess unanticipated grade 3 or higher toxicities (i.e. radiation pneumonitis, radiation dermatitis, radiation myelitis) prior to expansion of the cohorts.

TABLE OF CONTENTS

TITLE PAGE	1
DOCUMENT HISTORY	2
SYNOPSIS.....	3
TABLE OF CONTENTS.....	7
1 INTRODUCTION AND STUDY RATIONALE	11
1.1 Research Hypothesis.....	11
1.2 Study Rationale.....	11
1.2.1 Rationale for Nivolumab.....	11
1.2.2 Rationale for Combining SBRT with Nivolumab.....	12
1.2.3 Rationale for Combining Ipilimumab with SBRT and Nivolumab.....	13
1.2.4 Summary.....	13
1.3 Objectives(s)	13
1.3.1 Primary Objectives	14
1.3.2 Secondary Objectives.....	14
1.3.3 Exploratory Objectives	14
1.4 Rationale for Study Design	14
1.4.1 Rationale for Studying Merkel Cell Carcinoma.....	14
1.4.2 Immunotherapy for Merkel Cell Carcinoma.....	15
1.4.3 Rationale for ORR as Primary Endpoint with PFS and OS as a Secondary Endpoint.....	15
1.4.4 Rationale for Two Experimental Arm Design.....	15
1.4.5 Rationale for the Dose and Schedule for Nivolumab.....	16
1.4.6 Rationale for the Dose and Schedule for SBRT.....	16
1.4.7 Rationale for the Dose and Schedule for Ipilimumab.....	17

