9.1.1 Sample Size Calculation

From historical data, we will consider 17% response rate as not warranting further study. We will use 40% response rate as a promising result to pursue further study. In other words, we are interested in at least 23% (40% vs. 17%) improvement in treatment efficacy for arms B versus A. For each arm, using a Simon Mini-Max two-stage design with 10% type I error rate and 10% type II error rate, 16 patients will be enrolled in the first stage of the trial. If 2 or fewer patients respond, the treatment will be stopped. If 3 or more patients show a response, 8 additional patients (a total of 24 patients per group) will be enrolled. If the total number responding is 6 or less, we will conclude that the treatment is not effective. If both arms fail at the first or second stage, the trial will stop. No winner will be claimed. The sample size will be 32 if both arms fail at the first stage and 40 if only one arm fails at the first stage. If only one arm pass the second stage, the arm will be the winner. If both arms pass the second stage, we will use the posterior probability, $Pr(B > A)$, (probability of the response rate in arm B higher than in arm A) to select the winner. A non-informative prior of beta distribution, beta(1,1) in both arms will be used to calculate the posterior probability. Arm B will be claimed as the winner if $Pr(B > A) > \delta = 0.8$.

Operating Characteristics

The operating characteristics of the design is evaluated by simulation (10000 times) using R software (www.r-project.org) with "clinfun" package. In particular, we are interested in the probability of (correctly) selecting an arm as superior to the other arm if it is truly superior, and conversely, the probability of (incorrectly) selecting an arm that is no better than the other arm.

Power Analysis

Power: Assuming that the true probabilities of response in arms B and A are 40% and 17%, respectively (scenario 1: 23% difference of response rate), the overall probability (power) of correctly choosing arm B as superior is 85% on the basis of superiority shown at the end of the trial.

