The probability of stopping arm A early and declaring arm B superior at the end of the trial is 81%. There are 9% of both arms passing the second stage with 4% claiming arm B as the winner by the Bayesian posterior probability. In a 18% difference of response rate, the overall power is 74% and 77% for the comparison of arms B and A with 35% versus 17% (scenario 2) and 40% versus 22% (scenario 3), respectively. Proportion of both arms passing the 2nd stage is 8% in scenario 2 (scenario 3: 23%), with 2% (scenario 3: 10%) claiming arm B as the winner by the Bayesian posterior probability.

Type I error

Type I error: In the null hypothesis of a 17% response rate in both arms, there are 9% misclassifying arm B as winner (i.e., 9% type I error). Among them, only 1% has both arms passing the 2nd stage, and less than 0.01% misclassify arm B as winner.

Summary

Summary: With $\delta=0.8$, the design has a 85% power to detect a 23% difference of response rate. The power decreases to a range of 74-77% to differentiate a 18% difference of response rate. The type I error is controlled at 9% when both arms have a 17% response rate.

Tables of Power Analysis

Scenario 1: Arm B=0.4 versus Arm A=0.17 (Overall power of Arm B= 85%)

	B.fail.stage1	B.fail.stage2	B.pass
A.fail.stage1	0.01	0.04	0.42
A.fail.stage2	0.01	0.03	0.39
A.pass	0	0.01	0.09

Both arms passing the 2nd stage: 9%. Among them, Arm B claims 4.31% as winner

Overall power of Arm B= 85%

Scenario 2: Arm B=0.35 versus Arm A=0.17 (Overall power of Arm B= 74%)

	B.fail.stage1	B.fail.stage2	B.pass
A.fail.stage1	0.02	0.08	0.38
A.fail.stage2	0.02	0.07	0.33
A.pass	0	0.02	0.08

Both arms passing the 2nd stage: 8%. Among them, Arm B claims 2.33% as winner

Overall power of Arm B= 74%

Scenario 3: Arm B=0.4 versus Arm A=0.22 (Overall power of Arm B= 77%)

	B.fail.stage1	B.fail.stage2	B.pass
A.fail.stage1	0.01	0.03	0.25

A.fail.stage2	0.01	0.03	0.41
A.pass	0.01	0.02	0.23

Both arms passing the 2nd stage: 23%. Among them, Arm B claims 9.89% as winner

Overall power of Arm B= 77%

Scenario 4: Arm B=0.17 versus Arm A=0.17 (Type I error= 8.89%)

	B.fail.stage1	B.fail.stage2	B.pass
A.fail.stage1	0.22	0.2	0.04
A.fail.stage2	0.2	0.19	0.04
A.pass	0.05	0.04	0.01

Both arms passing the 2nd stage: 1%. Among them, Arm B claims 0.01% as winner

Type I error= 8.89%

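### The synopsis names a two-sided log-rank test as the primary analysis of ORR, which does not fit the endpoint and contradicts the plan's Simon and Pr(B>A) decision rule

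*Combined protocol and SAP*

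**What the plan says.** **Synopsis, Analyses.** "The primary analysis of ORR in all randomized subjects will be conducted using a two-sided log-rank test". Just before this: "All tests will be two-sided with an α (type I) error ≤ 0.05 considered to be statistically significant". Just after it comes a Cox hazard ratio with no endpoint named, then Kaplan-Meier medians and rates for PFS.

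**Synopsis, Study Assessments.** "The ORR will be calculated as the percentage of patients who had a complete or partial response", confirmed by later imaging or examination, "among all the patients who received at least one dose of nivolumab and ipilimumab with or without SBRT". The Endpoints entry of the same synopsis reads "Primary Endpoint: Objective response rate in all randomized subjects".

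**Synopsis, Statistical Considerations, and Section 9.1.1.** Each arm follows a Simon minimax design with 10% type I and 10% type II error. An arm stops at 2 or fewer responses in 16 and is judged ineffective at 6 or fewer in 24. Then "If only one arm pass the second stage, the arm will be the winner", and "If both arms pass the second stage, we will use the posterior probability", with beta(1,1) priors and a threshold of 0.8 for Arm B. Section 9.1.1 concludes that "the design has a 85% power to detect a 23% difference of response rate", with type I error of 9%.

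**Section 9.3.2.1 (Primary Endpoint Methods).** ORR is estimated with an exact binomial 95% interval among dosed patients. No log-rank test appears, and neither does the Simon and Pr(B>A) rule. Here and in 9.2.1, stable disease is counted in ORR.

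**Sections 9.2.2 and 9.3.2.2.** PD-L1 is an ORR objective in 1.3.2, but 9.2.2 measures it by RFS. Section 9.3.2.2 applies a Cox interaction, log-rank tests and hazard ratios to ORR by PD-L1 group. It also plans a between-arm log-rank test and hazard ratio for local control of irradiated lesions. The OS and local-control hazard ratios carry an interval at an adjusted alpha that is not defined anywhere.

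**The concern.** A log-rank test needs, for each patient, a time origin, an event time and a censoring rule. The plan defines these for PFS and OS but not for response. What it defines for ORR is a yes/no result per patient.

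The synopsis therefore holds two primary analyses: a significance test between arms at two-sided 0.05, and a pick-the-winner rule built on 10% errors against a 17% reference rate. They answer different questions and can give different answers. The trial is not blinded (Section 5), so an unresolved choice between them could be made after responses are known. The published operating characteristics would also be attached to an analysis they do not describe.

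**Working it through.** **1. Reproduce the stated figures.** Inputs from 9.1.1: 16 then 8 more patients per arm, pass with at least 3/16 and at least 7/24, beta(1,1) priors, threshold 0.8.

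Per arm, with X ~ Bin(16, p) and Y ~ Bin(8, p), the pass probability is the sum over x = 3 to 16 of Pr(X = x) × Pr(Y ≥ 7 − x).

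- At p = 0.17: stop at stage 1 0.472, pass 0.0978.
- At p = 0.40: stop at stage 1 0.018, pass 0.9013.

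Pr(B wins) = Pr(only B passes) + Pr(both pass and the posterior probability exceeds 0.8).

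- 40% v 17%: 0.9013 × (1 − 0.0978) = 0.8131. Both pass: 0.9013 × 0.0978 = 0.0881, of which B wins 0.0414. Total 0.8131 + 0.0414 = 0.8545.
- 17% v 17%: 0.0978 × 0.9022 + 0.0003 = 0.0885.

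| B v A | Stated | Exact |
|---|---|---|
| 40% v 17% | 85% | 85.4% |
| 35% v 17% | 74% | 73.3% |
| 40% v 22% | 77% | 76.6% |
| 17% v 17% | 8.89% | 8.85% |

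The protocol's values come from 10,000 simulations; the differences fit simulation error and rounding. A search for the minimax design at 17% v 40% with 10%/10% errors also returns 2/16 and 6/24. The stated figures belong to this rule.

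**2. Do they carry over to a two-sided 0.05 comparison?** This is illustration only, with 24 per arm, no stage 1 stopping and 40% v 17%.

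- Pooled z: the pooled rate is 0.285, and the standard errors are √(2 × 0.285 × 0.715/24) = 0.1303 and √((0.24 + 0.1411)/24) = 0.1260. Power = Φ((0.23 − 1.96 × 0.1303)/0.1260) = 42%. Exact enumeration gives 43% (Pearson) or 33% (Fisher).
- Log-rank on time to response, assuming exponential times and equal follow-up: expected responses 24 × 0.40 + 24 × 0.17 = 13.7; hazard ratio ln 0.60/ln 0.83 = 2.74; power = Φ(√(13.7/4) × ln 2.74 − 1.96) = 46%.

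They do not carry over.

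**3. Can the two analyses disagree?**

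- B 7/24, A 6/24: B wins because only B passes. Fisher p = 1.00; log-rank p = 0.75 if every response is placed at week 12 (assumed).
- B 10/24, A 7/24: Pr(B>A) = 0.811, so B wins. Pearson p = 0.37, Fisher p = 0.55.

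**4. Why pointing to 9.3.2.1 is not enough.** That section counts stable disease. If this added an assumed 5, 10 or 20 points to a true 17% rate, an arm's chance of passing would rise from 9.8% to 26.1%, 47.8% or 83.9% (the pass formula at p = 0.22, 0.27 and 0.37).

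**5. Secondary items.** Only Arm B receives SBRT (Section 4.1), so Arm A has no protocol-irradiated lesions and a between-arm hazard ratio for their control has no comparator. RFS is not defined as an endpoint. For PD-L1 by arm, counts will be small. Take 24 per arm, equal response across PD-L1 groups within an arm, 40% v 17%, and the protocol's own positivity of 75% (stage IV) or 53.8% (all stages), giving 18/6 or 13/11 per arm. If both arms pass stage 1, the chance that at least one of the four cells has no responders or only responders is about 25% or 6.5%.

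**The case against.** The strongest reply is that this is one stray sentence. The same synopsis gives the full decision rule, 9.1.1 repeats it with operating characteristics, and the section titled for the primary endpoint uses exact binomial methods. The neighbouring sentences and the near-identical PFS paragraph in 9.3.2.2 suggest carried-over PFS wording. The 0.05 sentence follows the toxicity comparison and may have been meant for that. Most of this stands, and the intent is fairly clear. But the sentence is labelled as the primary analysis, the 0.05 statement covers all tests, 9.3.2.1 does not itself state the decision rule, and 9.3.2.2 again applies log-rank methods to ORR.

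It is also fair to say that a pick-the-winner rule differs from a significance test by design. The discordant examples show only that the two texts are not interchangeable; they do not show a fault in the rule.

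Two stronger readings are tempting. A reader might infer that the trial is underpowered, at 33% to 46% instead of 85%. The documents do not support that: the sample size was derived for the Simon and Pr(B>A) rule and is right for it. A reader might also say that a log-rank test on response cannot be run at all. It can, once an event time and censoring rule are supplied; the plan supplies neither.

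**Conclusion.** The contradiction is real and needs correcting, because it concerns the named primary analysis. As written, the log-rank test is unspecified for ORR, does not match a percentage endpoint, and conflicts with the Simon and Pr(B>A) rule and its 10% design errors. The stated operating characteristics are sound, but only for that rule. The design, cut-offs and sample size are not in error.

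The reproduction assumes independent arms and full stage sizes of 16 and 24. The power figures for other tests, the stable-disease additions and the PD-L1 cell risks rest on the assumptions given with them and only show scale. The PD-L1, local-control and OS items are real but minor: the PD-L1 analyses are already labelled descriptive, Cox remains suitable there for PFS and OS, and Kaplan-Meier estimation of local control is already planned.

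**What to change.** **Primary analysis**

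- Synopsis, Analyses: delete the log-rank sentence for ORR and assign the log-rank and Cox text to PFS and OS, as in 9.3.2.2.
- Synopsis and 9.3.2.1: name as the primary analysis the Simon rule per arm, then Pr(B>A) > 0.8 if both arms pass, with an exact binomial 95% interval for each arm's ORR.
- State that two-sided 0.05 does not apply to the primary decision, which uses the 10% design error.
- Use one ORR definition: confirmed complete or partial response, with stable disease removed from 9.2.1 and 9.3.2.1 and reported separately if wanted. Reconcile the synopsis definition with the restriction to non-irradiated target lesions in Section 6 (opening), 6.5.4 and 9.2.1.
- State one analysis population, which patients make up the 16 and 24, and how a randomized but untreated patient counts.

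**Clean-up**

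- PD-L1: in 9.2.2 replace RFS with ORR. In 9.3.2.2 replace log-rank tests and hazard ratios on ORR with responder counts and exact intervals by PD-L1 group and arm; any interaction is descriptive.
- Local control: delete the between-arm test and hazard ratio. Estimate in Arm B only, with time origin, event and censoring stated.
- OS: replace the adjusted-alpha interval with a 95% interval.

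**Cost:** wording in the synopsis and in 9.2.1, 9.2.2, 9.3.2.1 and 9.3.2.2, plus decisions on the analysis population, the lesion restriction and the local-control definition. The 9.1.1 cut-offs, posterior rule, operating characteristics, sample size and data collection stay as they are.
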